9.2 Training of study site personnel

Before the first patient is entered into the study, an AstraZeneca representative (ICON) will review and discuss the requirements of the CSP and related documents with the investigational staff and also train them in any study specific procedures and the WBDC system utilised.

The Principal Investigator will ensure that appropriate training relevant to the study is given to all of these staff, and that any new information relevant to the performance of this study is forwarded to the staff involved.

The site staff will also be trained to use the electronic devices, training devices, ePRO web sites (Study Works), perform transmission, monitor e-diary compliance, handle queries and will be authorised to train patients in using the electronic devices and perform transmission prior to their participation in the study. The site staff will receive a detailed user manual for the use of the electronic device and the ePRO web sites. Retraining will be provided if needed. The investigators are not required to complete the full level training, if they will not train patients, nor assign nor use the electronic devices. Investigators will however, be trained to log into the web report system (Study Works) and follow the procedures for navigating to the patient data for their site. A training certificate will be issued to site staff participating in training at investigator meeting. Training of site staff outside the investigator meeting will be documented at the site level.

The site staff will be trained to use the dECG equipment and a detailed user manual will be included with the dECG equipment when delivered at the site.

The Principal Investigator will maintain a record of all individuals involved in the study (medical, nursing and other staff).

9.3 Monitoring of the study

During the study, an AstraZeneca representative (ICON) will have regular contacts with the study site, including visits to:

- Provide information and support to the investigator(s).
- Confirm that facilities remain acceptable.
- Confirm that the investigational team is adhering to the protocol, that data are being accurately and timely recorded in the eCRFs, that biological samples are handled in accordance with the Laboratory Manual and that IP accountability checks are being performed.
- Perform source data verification (a comparison of the data in the eCRFs with the patient's medical records at the hospital or practice, and other records relevant to the study) including verification of informed consent of participating patients. This will require direct access to all original records for each patient (eg, clinic charts).
- Ensure withdrawal of informed consent to the use of the patient's biological samples is reported and biological samples are identified and disposed of/destroyed accordingly, and the action is documented, and reported to the patient.

The AstraZeneca representative (ICON) will be available between visits if the investigator(s) or other staff at the centre needs information and advice about the study conduct.

9.3.1 Source data

Source data locations are specified in the CSA.

9.4 Study agreements

The Principal Investigator at each/the centre should comply with all the terms, conditions, and obligations of the CSA for this study. In the event of any inconsistency between this CSP and the CSA, the terms of CSP shall prevail with respect to the conduct of the study and the treatment of patients and in all other respects, not relating to study conduct or treatment of patients, the terms of the CSA shall prevail.

Agreements between AstraZeneca representative (ICON) and the Principal Investigator should be in place before any study-related procedures can take place, or patients are enrolled.

9.4.1 Archiving of study documents

The investigator follows the principles outlined in the CSA.

9.5 Study timetable and end of study

The end of the study is defined as "the last visit of the last patient undergoing the study".

The study is expected to start in Q4 2009 and to end by Q2 2010.

The study may be terminated at individual centres if the study procedures are not being performed according to GCP, or if recruitment is slow. AstraZeneca may also terminate the entire study prematurely if concerns for safety arise within this study or in any other study with AZD3355.

10. DATA MANAGEMENT BY ASTRAZENECA REPRESENTATIVE (ICON)

Data management will be performed by AstraZeneca representative (ICON). Data will be entered in the WBDC system at the study site. Trained study personnel will be responsible for entering data on the observations, tests and assessments specified in the protocol into the WBDC system and according to the eCRF Instructions. The eCRF instructions will also provide the study site with data entry instructions. Data queries will be raised for inconsistent, impossible or missing data. Data entered in the WBDC system will be immediately saved to a central database and will be available in an audit trail. When data have been entered, reviewed, edited and Source Data Verification (SDV) performed, the Principal Investigator will be notified to sign the eCRF electronically as per the agreed project process and data will be locked to prevent further editing.

Data collected from the completed eCRFs, laboratory data and through third party sources will be received electronically by an AstraZeneca representative (ICON) and reconciled against study data. The process will be documented in the Data Management Plan and the validation performed under the direction of the responsible Data Manager, according to the Data Validation Manual. Quality control procedures will be applied to each stage of data handling to ensure that all data are reliable and have been processed correctly.

AEs and medical history/surgical history will be classified according to the terminology of the latest version of the Medical Dictionary for Regulatory Activities (MedDRA). Medications will be classified according to the AstraZeneca Drug Dictionary. All coding will be done performed by an AstraZeneca representative (ICON). Queries can be raised by the coding expert at any time during the study period and the query tool in RAVE will be used. When all data have been coded, validated, signed and locked, clean file will be declared. Any treatment revealing data may thereafter be added and the final database will be locked.

The central ECG vendor (ERT) will be used to collect dECG data and sites will transmit the dECG data to ERT's central database using equipment provided by the vendor. ERT will identify, examine and analyse the data and will send the ECG reports to site. See Section 6.4.7.

Laboratory data will be delivered to an AstraZeneca representative (ICON) by the central laboratory (Quintiles). The laboratory data will be loaded into the study database.

The ePRO system is a specialised data capture appliance designed for entry of data in a way that is attributable, secure and accurate in compliance with FDA's Final Rule: Electronic Records; Electronic Signature (21 CFR part 11). The ePRO system will be provided by a central vendor (PHT Corporation). The ePRO data will be transmitted either via analog or wireless modems to a central database.

After the ePRO data have been received at the central database, it can be reviewed via a secure access to a web-server. All data will be date and time stamped and all changes will be tracked in the systems audit trail. Each user needs to have system training before any access will be given out. All actions on data are to be accomplished using the system controls compliant with 21 CFR part 11 that are built in to the system application used to collect, clean, review and archive clinical study data.

The investigators (or study personnel designated by the investigator) are responsible for any modification of data on study patients. No changes to the patient's symptom recording should be made. Investigators, study monitors, (and any auditors or FDA inspectors) will have access to the data and electronic records via connection to the web-server from the site. Clinical investigators shall retain the recordings during the study in the sense that they can access them and they uniquely and specifically control the contents of the data in the records.

Online study reports will be accessible to the study team during the study. The source files will be returned to AstraZeneca R&D, Mölndal.

For information regarding genetic data, see [Appendix D](#).

11. EVALUATION AND CALCULATION OF VARIABLES BY ASTRAZENECA

11.1 Calculation or derivation of efficacy variable(s)

Efficacy variables will be based on patient reported outcomes. Therefore, see section [11.3](#) for derivation of efficacy variables.

11.2 Calculation or derivation of safety variable(s)

11.2.1 Other significant adverse events (OAE)

During the evaluation of the AE data, an AstraZeneca medically qualified expert will review the list of AEs that were not reported as SAEs and Discontinuation of IP due to Adverse Events (DAE)s. Based on the expert's judgement, significant AEs of particular clinical importance may, after consultation with the Global Patient Safety Physician, be considered OAEs and reported as such in the CSR. A similar review of laboratory/vital signs/ECG data will be performed for identification of OAEs.

Examples of these are marked haematological and other laboratory abnormalities, and certain events that lead to intervention (other than those already classified as serious), dose reduction or significant additional treatment.

11.3 Calculation or derivation of patient reported outcome variables

11.3.1 Reflux Symptom Questionnaire e-diary

The RESQ-eD consists of 13 items that combine into an Overall symptoms domain and 4 separate domains:

- Heartburn
 - burning feeling behind the breastbone
 - pain behind the breastbone
 - heartburn
 - burning feeling in centre of the upper stomach
 - pain in centre of the upper stomach
- Regurgitation
 - acid taste in the mouth
 - bitter taste in the mouth
 - unpleasant movement of material upwards from the stomach
 - stomach contents (liquid or food) moving upwards to your throat and mouth
- Hoarseness, cough and difficulty swallowing
 - hoarseness
 - cough
 - difficulty swallowing
- Burping
 - Burping.

The e-diary ratings of the 6-graded Likert scale are transformed to numerical values, from “Did not have” = 0 to “Severe” = 5.

When imputing missing values, morning registrations will be regarded as one sequence of observations and evening registrations as another sequence of observations. Missing values in the sequence of morning or evening registrations respectively will be imputed according to the following rules. If a single observation is missing, the missing value will be replaced by the larger of the two surrounding values. If two or more consecutive observations are missing the values will remain missing.

Values of intensity for a day (approximately a 24 h period) will then be constructed using the imputed sequences of evening and morning registrations of item intensities. A day will consist of an evening and the following morning registration. The daily item intensity will be defined as the maximum of the two registrations. If either the morning or the evening registration is missing, the corresponding daily value will be set to missing in the statistical analyses. In the algorithm determining whether a patient is eligible for randomization missing values are not imputed, and the daily value will be the maximum value of the evening and morning registration even if one of them is missing.

The domain intensity on a given day will be derived as the mean daily intensities of the items that form the domain.

The proportion of days of not more than mild symptoms with respect to a domain during a specified time period will be calculated as: the number of days when none of the items in the domain has a daily intensity that exceeds “Mild” (numerical value 2) divided by the number of expected values in the specified time period. That is, a day with missing value will be regarded as a day with more than mild symptoms.

Baseline will be defined as the seven days prior to visit 2 (Randomization visit). Hence, the last e-diary registration that contributes to the baseline period will be the morning registration on the day of visit 2.

A patient’s treatment period will be defined as the days from the day of first dose up to and including the day of last dose. Hence, the first e-diary registration contributing to the treatment period will be the evening registration on the day of the first dose, and the last e-diary registration contributing to the treatment period will be the morning registration on the day of the last dose. If the date of the first dose has not been entered in the database, the date of the first dose will be imputed to the date of visit 2 (Randomization visit). If the date of the last dose has not been entered in the database, the date of the last dose will be imputed to the date of visit 6 (End of treatment visit).

The change from baseline to the treatment period in proportion of days of not more than mild symptoms with respect to a domain will be calculated as the proportion of days of not more than mild symptoms with respect to the domain during the patient’s treatment period minus the proportion of days of not more than mild symptoms with respect to the domain during the patient’s baseline period.

Primary outcome variable:

A responder is defined as a patient who experiences at least three more days of not more than mild symptoms on average per week during treatment compared to baseline, based on the Overall symptoms domain in the RESQ-eD. This means that the increase from baseline to the treatment period in the proportion of days of not more than mild symptoms will exceed or equal 3/7 for a responder. A patient that is not classified as a responder according to this criteria will be classified as a non-responder. The primary outcome variable is the binary variable (yes/no) indicating a patient who meets the responder definition.

Secondary outcome variables:

An alternative definition of a responder is a patient who experiences at least five days of not more than mild symptoms on average per week during treatment, based on the Overall symptoms domain in the RESQ-eD. This means that the proportion of days of not more than mild symptoms during the treatment period will exceed or equal 5/7 for a responder. A patient that is not classified as a responder according to these criteria will be classified as a non-responder. A secondary outcome variable is the binary variable (yes/no) indicating a patient who meets the alternative responder definition.

The change from baseline to the treatment period in proportion of days of not more than mild symptoms, as defined above, with respect to the Overall symptoms domain, the Heartburn domain, the Regurgitation domain, the Hoarseness, cough, difficulty swallowing domain and the Burping domain will be analysed as secondary outcome variables.

For the assessment of basic measurement properties of the RESQ-eD the following variables will be derived:

- Item intensity over baseline will be derived as the mean of the daily item intensities during the seven days that form the baseline period.
- Domain intensity over baseline will be derived as the mean of the daily domain intensities during the seven days that form the baseline period. If more than two daily domain intensity values are missing during the seven day period for a patient, the baseline intensity will be set to missing.
- Domain intensity over the seven days prior to visit 4 will be derived as the mean of the daily domain intensities during the seven days. The last e-diary registration that contributes to the seven day period will be the morning registration on the day of visit 4. If more than two daily domain intensity values are missing during the seven day period for a patient, the intensity for the seven days prior to visit 4 will be set to missing.
- Domain intensity over the treatment period will be derived as the mean of the daily domain intensities during the treatment period. If the patient has less than 7 days on treatment or if more than 30% of the daily domain intensity values

during treatment are missing then the domain intensity over the treatment period will be set to missing.

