2. STUDY OBJECTIVES

2.1 Primary objective

The primary objective is to evaluate the effect on GERD symptoms of four doses of AZD3355 (60 mg, 120 mg, 180 mg and 240 mg bid) compared to placebo, as add-on treatment to a PPI by using the responder definition; ie, at least 3 more days of not more than mild GERD symptoms on average per week during the whole treatment period compared to baseline, based on the Overall symptoms domain in the RESQ-eD.

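### Both responder variables are computed over each patient's own dosed days with no minimum duration, so an early stopper can be a responder on one good day

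*Protocol*

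**What the plan says.** Section 2.1 defines response as a gain in good days "on average per week during the whole treatment period compared to baseline", in a trial with 4 weeks of treatment (3.1).

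Section 11.3.1 then fixes the calculation:

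- The treatment period is the "treatment period will be defined as the days from the day of first dose up to and including the day of last dose". In diary terms, "the last e-diary registration contributing to the treatment period will be the morning registration on the day of the last dose".
- The proportion is the count of good days "divided by the number of expected values in the specified time period".
- Within that period, "a day with missing value will be regarded as a day with more than mild symptoms".
- For the primary variable, "the increase from baseline to the treatment period in the proportion of days of not more than mild symptoms will exceed or equal 3/7 for" any patient classed as responding. The alternative definition requires an on-treatment proportion of at least 5/7. Anyone who does not meet a definition is a non-responder.

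The same section does set a minimum for another variable. Domain intensity over the treatment period, used only to assess measurement properties, is set to missing under the condition "If the patient has less than 7 days on treatment or if more than 30% of the daily domain intensity values" (the second part refers to missing values on treatment).

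All randomized patients with at least one dose enter the full analysis set (12.1.1), and the diary device is returned at discontinuation (5.8.1).

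**The concern.** Days after the last dose are not expected values, so the rule that scores a missing day as symptomatic never reaches them. A patient who stops in the first days is judged on those days alone, against the same 3/7 or 5/7 threshold as a patient observed for 4 weeks. A proportion from a handful of days crosses a threshold by chance more easily than one from 28 days when the patient's true level lies below it.

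Section 5.8 lists criteria that force discontinuation, including syncope, severe dizziness, QTcF and liver tests, so more stopping at higher doses is foreseeable. The highest dose is tested first and opens the step-down (12.2.2). A rule that lets early stoppers respond too easily would act there.

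A smaller point comes from the same sentence. It covers any time period, so a missing baseline day also counts as symptomatic. That lowers the baseline value that is subtracted and makes a response easier.

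**Working it through.** **1. The plan's own figure.** Section 12.3 gives 24% against 39%, 130 per arm, a one-sided chi-square test at 10% and about 90% power. Recalculation gives 91.0%. The smallest significant difference is 10/130 = 7.7%, matching the stated 8%. The sample size is not in question.

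**2. Good days needed.** I read expected values as evening-plus-morning pairs, so a last dose on the day after the first dose gives one evaluable day. With b good baseline days of 7 and n evaluable treatment days, the number needed is ceil(n × (b + 3)/7). Inclusion criterion 10 requires at least 3 of 7 days of at least moderate intensity on one of two items, both in the Overall domain, so b is at most 4.

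| n | b=0 | b=1 | b=2 | b=3 | b=4 |
|---|---|---|---|---|---|
| 1 | 1 | 1 | 1 | 1 | 1 |
| 2 | 1 | 2 | 2 | 2 | 2 |
| 3 | 2 | 2 | 3 | 3 | 3 |
| 7 | 3 | 4 | 5 | 6 | 7 |
| 28 | 12 | 16 | 20 | 24 | 28 |

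At n = 1 one good day suffices for every eligible patient, because 1 − 4/7 = 3/7. The alternative definition behaves alike: ceil(5n/7) is 1 at n = 1 and 20 at n = 28. This step needs no assumption about dropout.

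**3. How often a stopper would respond.** Assume b = 1 and day probabilities that vary between patients (beta-binomial), calibrated to 24% response over 28 days.

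| Within-patient correlation | 3 days | 5 days | 7 days |
|---|---|---|---|
| 0.2 | 35% | 33% | 32% |
| 0.5 | 28% | 27% | 27% |

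The inflation is not uniform. Because the number needed is rounded up, b = 1 with 2 days gives 19% at either correlation, and b = 0 with 3 days gives 21-22%, both below 24%.

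**4. Effect on the responder test with no drug effect.** Response in an arm = 0.24 × (1 − d) + d × r, where d is the share stopping early and r is their response rate. The protocol gives no dropout rate, so d is assumed; r runs from 28% to 35%. Exact rejection rates with 130 per arm, one-sided 10%:

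| d active / placebo | Spurious difference | Rejection rate |
|---|---|---|
| 10% / 4% | 0.06 × (4 to 11 points) = 0.2 to 0.7 points | 11-12% |
| 15% / 4% | 0.11 × (4 to 11 points) = 0.4 to 1.2 points | 12-15% |
| 20% / 5% | 0.15 × (4 to 11 points) = 0.6 to 1.7 points | 12-17% |

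**5. Baseline.** Each missing baseline day that was truly good lowers the hurdle by 1/7, which is 4 good days of 28. A true 4/7 needs 28 of 28; with two of those good days missing it is scored 2/7 and needs 20 of 28. A missing day that was really symptomatic changes nothing.

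**The case against.** **A while-on-treatment estimand is legitimate.** Section 11.3.1 defines the period explicitly, and tolerability is assessed alongside efficacy when the dose is chosen (1.3). This stands, but it does not explain why one day should count as a response, and the plan sets a 7-day minimum for a less important variable.

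**Short windows also hurt.** At baseline 1/7, a patient with a 0.40 daily chance of a good day responds with probability 5% over 28 days and 35% over 3. With a daily chance of 0.70 the figures are 95% and 78%. The first patient alone would overstate the effect.

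**Few stops should be that early.** The paraesthesia criterion needs 7 consecutive days, and after visit 2 scheduled ECGs and liver tests resume only at about week 1. A dose group stopped for safety leaves the primary efficacy comparison (12.2.1). These points limit the size.

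**Stronger readings the document does not support:**

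- That the E-max curve is pushed upward. It models the change in proportion (12.2.3.3). With a constant daily chance, the expected proportion does not depend on window length.
- That the rule turns a true +8 to +12 points into +15. With assumed rates of 39% against 24% and the stopping rates above, scoring every stopper as a non-responder gives, for example, 0.39 × 0.80 − 0.24 × 0.95 = 8.4 points. That is a different estimand, not a measure of error.
- That a patient with no evaluable day is unclassified. For the binary variables the catch-all sentence makes that patient a non-responder.
- That missing baseline days favour active drug. They arise before randomization and should balance across arms. Section 3.1 asks for 7 evening and 7 morning reports, and single gaps are imputed. They remain possible, because in the eligibility algorithm "the daily value will be the maximum value of the evening and morning registration even if one of them is missing".

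**Conclusion.** The point holds for the two binary responder variables. The definition lets an early stopper be a responder on as little as one good day, while the objective speaks of the whole treatment period. That follows from the text and eligibility alone.

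The consequence for the test is modest: a null rejection rate of about 11-17% instead of 10%. The upper end needs 20% against 5% stopping and stoppers responding at 35%. Dropout, its imbalance across doses and within-patient correlation are all assumed. With balanced stopping there is misclassification but little bias between arms.

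The baseline rule is a minor misclassification that eases response in all arms. Severity: should-fix, because the endpoint is primary and the repair is short.

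**What to change.** In section 11.3.1, for both responder variables, adopt one of these before unblinding:

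1. Class patients with fewer than 7 treatment days, including those with no evaluable day, as non-responders. This borrows the 7-day limit from the domain-intensity rule, which sets a value to missing, so non-response must be stated in its own right.
2. For patients who stop early, count planned days after the last dose up to day 28 as more than mild. A patient with baseline 0/7 then needs 12 good days, so anyone with fewer than 12 evaluable days cannot respond. Completers whose visit 6 falls early within its window should not be penalised.

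Keep the own-days version as a sensitivity analysis. Add a second one with the baseline proportion taken over recorded baseline days.

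The cost is a few sentences and two sensitivity tables. Some patients who did well and then stopped become non-responders, so responder rates fall slightly, and power falls if dropout is unbalanced. As an outer bound, if every stopper at any time became a non-responder under 24% against 39%, power would fall from 91% to 81% (10% / 4% stopping) or 60% (20% / 5%). Option 1 touches only those who stop in the first week and should cost much less.
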